Medications taken after the first dose of study medication and through the last study-related activity will be documented on the appropriate CRF as concomitant medication. Prior and concomitant medications to be documented include but are not limited to: vitamins, herbal remedies (e.g., St. John's wort, valerian), over the counter and prescription medications.

Subjects will be instructed not to take any concomitant medication without first consulting the investigator or study coordinator throughout the duration of the study.

Prohibited Concomitant Medications:

The following medications and therapies are prohibited throughout the study (from signing of informed consent form [ICF] through the last study-related activity):

- Use of hormonal medications such as hormone therapy, HRT or hormonal contraception or any treatment for menopausal symptoms (prescription, over the counter or herbal).
- Investigational research products that have not been approved for any indication in the country where the subject is enrolled.
- Strong or moderate CYP1A2 inhibitors are prohibited.

Duration of Treatment:

Subject will take study drug daily from day 1 (randomization) for a duration of 52 weeks.

Formal Stopping Rules

Subject Discontinuation:

A subject **must** be withdrawn from the study treatment for any of the following reasons:

- Withdrawal of informed consent.
- Lost to follow-up.
- If for safety reasons it is in the best interest of the subject that she be withdrawn, in the investigator's opinion.
- Development of a medical condition that requires concomitant treatment with a prohibited therapy.
- Development of seizures or other convulsive disorders.
- Breaking of the randomization code during administration of the study drug by the investigator or by a member of the site staff. If the code is broken by the sponsor for safety reporting purposes or early time point analysis, the subject may remain in the study.
- Confirmed (within 72 hours from the notification of test result) decrease in platelets below 75,000 mm³, which does not normalize after 7 days or immediate withdrawal in case of platelets below 50,000 mm³.
- Development of severe hepatic abnormality defines as ALT or AST > 8 × ULN.
- Confirmed (within 72 hours from the notification of test result) severe hepatic abnormality defined as any of the following:
 - ALT or AST > 5 × ULN for more than 2 weeks;
 - ALT or AST > 3 × ULN **AND** TBL > 2 × ULN or INR > 1.5; or

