- Safety laboratory tests collected at a local lab including biochemistry, hematology, liver biochemistry and coagulation panel testing.
- Home healthcare services may be available in cases where arrangements are made in advance by the site upon request from the subject(s)

Due to the nature of the Screening (visit 1), Randomization, week 0 (visit 2) and EOT/ED week 52 (visit 15) visits, which include important study procedures, these visits must be conducted in the clinic. All other visits during the COVID-19 pandemic may be conducted utilizing all or some of the following services: home healthcare, telemedicine conferences (telephone visits) or safety laboratory tests collected at a local laboratory.

Subjects who screen failed due to the COVID-19 pandemic study suspension and have a documented evaluable endometrial biopsy from the original screening period do not have to undergo a repeat biopsy should they decide to rescreen.

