5.4.3 Laboratory Assessments

Below is a table of the laboratory tests that will be performed during the conduct of the study. See [[Table 1 Schedule of Assessments](#)] for study visit collection dates.

Urine Pregnancy Test	β -HCG
Hematology	CBC: white blood cell count with differential (neutrophils, lymphocytes, eosinophils, monocytes, and basophils) hemoglobin hematocrit red blood cell count platelets reticulocytes
Biochemistry	Blood urea nitrogen Chloride Creatinine Inorganic phosphorus Sodium Bicarbonate Calcium Creatine kinase Estimated glomerular filtration rate Glucose Lactate dehydrogenase Potassium Uric acid
Table continued on next page	

Urine Pregnancy Test	β -HCG
Liver Biochemistry	Alanine aminotransferase Alkaline phosphatase Aspartate aminotransferase Albumin Gamma-glutamyltransferase Total bilirubin Direct bilirubin
Urinalysis	Protein Glucose pH Blood
Coagulation Panel	International normalized ratio Activated partial thromboplastin time Prothrombin time
Serology	HBsAg HCV antibody HIV antibody Anti-HBs Anti-HBc
Hormone Levels	LH FSH Estradiol SHBG Testosterone Total/Free Androstenedione DHEA Estrone

anti-HBc: antibody to hepatitis B core antigen; anti-HBs: antibody against hepatitis B antigen; β -HCG: beta human chorionic gonadotropin; BSAP: bone specific alkaline phosphatase; CBC: complete blood count; DHEA: dehydroepiandrosterone; FSH: follicle-stimulating hormone; HBsAG: hepatitis B virus surface antigen; HCV: hepatitis C virus; HIV: human immunodeficiency virus; LH: luteinizing hormone; SHBG: sex hormone-binding globulin

If the clinical laboratory results are outside the normal range, the investigator will document his/her assessment as clinically significant or not clinically significant.

Unscheduled tests or a repeat of abnormal laboratory test(s) may be performed if clinically indicated and to follow-up on suspected AEs.

Laboratory normal ranges will be outlined in the Laboratory manual and will be provided to all participating centers.

Clinical significance of out-of-range laboratory findings is to be determined and documented by the investigator/subinvestigator who is a qualified physician.

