5.8.2 Definition of Serious Adverse Events (SAEs)

An AE is considered “serious” if, in the view of either the investigator or sponsor, it results in any of the following outcomes:

- Results in death;
- Is life-threatening (an AE is considered “life-threatening” if, in the view of either the investigator or sponsor, its occurrence places the subject at immediate risk of death. It does not include an AE that, had it occurred in a more severe form, might have caused death);
- Results in persistent or significant disability/incapacity or substantial disruption of the ability to conduct normal life functions;
- Results in congenital anomaly, or birth defect;
- Requires inpatient hospitalization (except for planned procedures as allowed per study) or leads to prolongation of hospitalization (except if prolongation of planned hospitalization is not caused by an AE). Hospitalization for treatment/observation/examination caused by AE is to be considered as serious);
- Discontinuation due to increases in liver enzymes [[Section 6.1](#)]; and
- Other medically important events (defined in paragraph below).

Medical and scientific judgment should be exercised in deciding whether expedited reporting is appropriate in other situations, such as important medical events that may not be immediately life-threatening or result in death or hospitalization but may jeopardize the subject or may require intervention to prevent one of the other outcomes listed in the definition above. These events, including those that may result in disability/incapacity, usually are considered serious. Examples of such events are intensive treatment in an emergency room or at home for allergic bronchospasm; blood dyscrasias or convulsions that do not result in hospitalization; or development of drug dependency or drug abuse.

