6 DISCONTINUATION

6.1 Discontinuation of Individual Subject(s) From Study Treatment

A discontinuation from treatment is a subject who enrolled in the study and for whom study treatment is permanently discontinued for any reason. The reason for discontinuation from study treatment must be documented in the subject's medical records.

A subject **must** discontinue study treatment for any of the following reasons:

- Withdrawal of informed consent
- Lost to follow-up
- If, for safety reasons, it is in the best interest of the subject that she be withdrawn, in the investigator's opinion
- Development of a medical condition that requires concomitant treatment with a prohibited therapy
- Development of seizures or other convulsive disorders
- Breaking of the randomization code during administration of the study drug by the investigator or by a member of the site staff. If the code is broken by the sponsor for safety reporting purposes or early time point analysis, the subject may remain in the study.
- Confirmed (within 72 hours from the notification of test result) decrease in platelets below 75,000 mm³, which does not normalize after 7 days or immediate withdrawal in case of platelets below 50,000 mm³.
- Development of severe hepatic abnormality defined as ALT or AST > 8 × ULN
- Confirmed (within 72 hours from the notification of test result) severe hepatic abnormality for any of the following:
 - ALT or AST > 5 × ULN for more than 2 weeks;
 - ALT or AST > 3 × ULN **AND** TBL > 2 × ULN or INR > 1.5 × ULN, and INR > 1.5; or

- ALT or AST $> 3 \times$ ULN with the appearance of fatigue, nausea, vomiting, right upper quadrant pain or tenderness, fever, rash and/or eosinophilia ($> 5\%$ increase from baseline).
- The subject becomes pregnant.
- Category 2 results of secondary or tertiary screening endometrial biopsy diagnosis.

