8.3 Major Protocol Deviations

A protocol deviation is generally an unplanned excursion from the protocol that is not implemented or intended as a systematic change. Deviations from the protocol are to be recorded. A protocol waiver is a documented prospective approval of a request from an investigator to deviate from the protocol. Protocol waivers are strictly prohibited.

The investigator is responsible for ensuring the study is conducted in accordance with the procedures and evaluations described in this protocol and must protect the rights, safety and well-being of subjects. The investigator should not implement any deviation from, or changes of, the protocol, unless it is necessary to eliminate an immediate hazard to subjects.

A major protocol deviation is 1 that may potentially impact the completeness, accuracy or reliability of data contributing to the primary endpoint or affect the rights, safety or well-being of a subject. Major protocol deviations will have additional reporting requirements.

When a major deviation from the protocol is identified for an individual subject, the investigator or designee must ensure the sponsor is notified. The sponsor will follow up with the investigator, as applicable, to assess the deviation and the possible impact to the safety

and/or efficacy or pharmacokinetic parameters of the subject to determine subject continuation in the study.

The major protocol deviation criteria that will be summarized at the end of the study are as follows:

PD1 - Entered into the study even though the subject did not satisfy entry criteria

PD2 - Developed withdrawal criteria during the study and was not withdrawn

PD3 - Received wrong treatment or incorrect dose

PD4 - Received excluded concomitant treatment

The investigator will also assure that deviations meeting IRB/IEC and appropriate regulatory authorities' criteria are documented and communicated appropriately. All documentation and communications to the IRB/IEC and appropriate regulatory authorities will be provided to the sponsor and maintained within the Trial Master File.

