12.5 Liver Safety Monitoring and Assessment

Any subject enrolled in a clinical study with active drug therapy and reveals an increase of serum aminotransferases (AT) to $> 3 \times \text{ULN}$ or bilirubin $> 2 \times \text{ULN}$ should undergo detailed testing for liver enzymes (including at least ALT, AST, ALP and TBL). Testing should be repeated within 72 hours of notification of the test results. For studies for which a central laboratory is used, alerts will be generated by the central laboratory regarding moderate and severe liver abnormality to inform the investigator and study team. Subjects should be asked if they have any symptoms suggestive of hepatobiliary dysfunction.

Definition of Liver Abnormalities

Confirmed abnormalities will be characterized as moderate and severe where ULN:

	ALT or AST		TBL
Moderate	$> 3 \times \text{ULN}$	or	$> 2 \times \text{ULN}$
Severe	$> 3 \times \text{ULN}$	and	$> 2 \times \text{ULN}$

In addition, the subject should be considered to have severe hepatic abnormalities for any of the following:

- ALT or AST $> 8 \times \text{ULN}$;
- ALT or AST $> 5 \times \text{ULN}$ for more than 2 weeks;
- ALT or AST $> 3 \times \text{ULN}$ **AND** TBL $> 2 \times \text{ULN}$ or INR > 1.5 ; or
- ALT or AST $> 3 \times \text{ULN}$ with the appearance of fatigue, nausea, vomiting, right upper quadrant pain or tenderness, fever, rash and/or eosinophilia ($> 5\%$ increase above baseline).

The investigator may determine that abnormal liver test results, other than as described above, may qualify as moderate or severe abnormalities and require additional monitoring and follow-up.

Follow-up Procedures

Confirmed moderate and severe abnormalities in hepatic tests should be thoroughly characterized by obtaining appropriate expert consultations, detailed pertinent history, physical examination and laboratory tests. The site staff is to complete the liver abnormality case report form (LA-CRF). Subjects with confirmed liver aminotransferases (ALT or AST) should be followed as described below.

Confirmed moderately abnormal liver tests should be repeated 2 to 3 times weekly then weekly or less if abnormalities stabilize or the study drug has been discontinued and the subject is asymptomatic.

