- ALT or AST $> 3 \times$ ULN and TBL $> 2 \times$ ULN or INR $> 1.5 \times$ ULN, and INR ;
- ALT or AST $> 3 \times$ ULN with the appearance of fatigue, nausea, vomiting, right upper quadrant pain or tenderness, fever, rash and/or eosinophilia ($> 5\%$ increase above baseline).

Subjects who develop a signal for liver injury will be monitored every 2 to 4 weeks if the study drug is discontinued. If the subject remains on study drug, they will be closely monitored for liver biochemistry results.

Subjects with a signal of elevated ($> 3 \times$ ULN) transaminases will have pharmacokinetic samples drawn in addition to repeat blood draws for liver biochemistry monitoring. These samples can be held for potential analysis based on the subject’s clinical outcome.

In addition, if close monitoring for a subject with moderate or severe hepatic laboratory tests is not possible, study treatment should be discontinued.

***Hy's Law Definition:** Drug-induced jaundice caused by hepatocellular injury, without a significant obstructive component, has a high rate of bad outcomes, from 10 to 50% mortality (or transplant).

The 2 "requirements" for Hy's Law are:

1. Evidence that a drug can cause hepatocellular-type injury, generally shown by an increase in transaminase elevations higher $3 \times \text{ULN}$ ($2 \times \text{ULN}$ elevations are too common in treated and untreated patients to be discriminating).
2. Cases of increased bilirubin (at least $2 \times \text{ULN}$) in people with concurrent transaminase elevations to at least $3 \times \text{ULN}$ (but it is almost invariably higher) and no evidence of intra- or extra-hepatic bilirubin obstruction (elevated ALP) or Gilbert's syndrome [Temple, 2006].

FDA Guidance for Industry titled "Drug-induced Liver Injury: Premarketing Clinical Evaluation" issued by the FDA on July 2009:

FDA Guidance for Industry:

1. The drug causes hepatocellular injury, generally shown by a higher incidence of 3-fold or greater elevations above the ULN of ALT or AST than the (nonhepatotoxic) control drug or placebo.
2. Among trial subjects showing such AT elevations, often with ATs much greater than $3 \times \text{ULN}$, one or more also show elevation of serum TBL to $> 2 \times \text{ULN}$, without initial findings of cholestasis (elevated serum ALP).

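### The mandatory combined liver stop in Protocol 6.1 has a looser INR threshold than the Synopsis and the Appendix 12.5 severe definition whenever the laboratory's INR upper limit exceeds 1.0

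*Protocol*

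**What the plan says.** The criterion appears in four places in the current protocol. In each it is conditional on ALT or AST above 3 × ULN.

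- Synopsis, Formal Stopping Rules (mandatory withdrawal from treatment): "TBL > 2 × ULN or INR > 1.5; or".
- Section 6.1 (mandatory discontinuation): "TBL > 2 × ULN or INR > 1.5 × ULN, and INR > 1.5; or".
- Section 12.5, definition of severe abnormality: "TBL $> 2 \times \text{ULN}$ or INR > 1.5".
- Section 12.5, mandatory treatment discontinuation: "INR $> 1.5 \times$ ULN, and INR". No value follows the second INR in the text available to me. That may be a reading fault, so nothing below rests on how the line ends.

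Amendment 3 does not touch this criterion, so the difference is not between superseded and current wording. No rule says which list governs. Section 1.5 refers the reader to 12.5 for liver assessment. The SAE definition in 5.8.2 refers to 6.1 for "Discontinuation due to increases in liver enzymes". The INR reference range is not given; Section 5.4.3 says "Laboratory normal ranges will be outlined in the Laboratory manual".

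**The concern.** The protocol names liver injury as an important potential risk (Section 1.5) and lists individual stopping rules among the controls for it. One of those rules is written with an absolute INR limit in one list and with a limit scaled to the laboratory's upper limit in another. If that upper limit is above 1.0, the scaled form is the less protective one.

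The mismatch also splits a single term. Section 6.1 introduces its list as severe hepatic abnormality, and 12.5 defines that term with INR > 1.5. A patient could therefore be severe under 12.5 and still miss the INR part of the 6.1 stop.

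Two things are at stake. One is whether treatment is stopped promptly for that individual. The other is whether leaving her on treatment counts under "PD2 - Developed withdrawal criteria during the study and was not withdrawn".

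**Working it through.** No figure in the plan needs reproducing; the check compares the two rules as logical conditions.

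**Inputs.** The Synopsis and 6.1 wordings are as quoted. The INR upper limit (U) is not in the documents, so I assume values from 0.9 to 1.3. ALT or AST above 3 × ULN is taken as already confirmed. Bilirubin and INR are read as alternatives beneath that condition.

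**Formulas, with bilirubin at or below 2 × ULN.**

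- Synopsis: stop if INR > 1.5.
- Section 6.1: stop if INR > 1.5 × U and INR > 1.5, which is INR > max(1.5, 1.5 × U).

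| Assumed U | 1.5 × U | 6.1 threshold | Synopsis threshold | INR values where only the Synopsis stops | Patient with INR 1.6: Synopsis / 6.1 |
|---|---|---|---|---|---|
| 0.9 | 1.35 | 1.50 | 1.50 | none | stop / stop |
| 1.0 | 1.50 | 1.50 | 1.50 | none | stop / stop |
| 1.1 | 1.65 | 1.65 | 1.50 | above 1.50 to 1.65 | stop / no stop |
| 1.2 | 1.80 | 1.80 | 1.50 | above 1.50 to 1.80 | stop / no stop |
| 1.3 | 1.95 | 1.95 | 1.50 | above 1.50 to 1.95 | stop / no stop |

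The gap is 1.5 × (U − 1.0) when U exceeds 1.0: 0.15, 0.30 and 0.45 in the last three rows. At U of 1.0 or below, the extra INR > 1.5 clause acts as a floor and the lists agree.

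**Who falls in the gap.** The patient must meet no other liver stop. ALT or AST is above 3 but not above 8 × ULN, and not above 5 × ULN for more than 2 weeks. Bilirubin is not above 2 × ULN. None of the listed symptoms, nor the eosinophil rise, is present. INR lies inside the band in the table.

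**How common that might be.** In the phase 2b study (Sections 1.4.2 and 2.2.2), 9 subjects exceeded 3 × ULN and 7 of them took 120 mg a day or more. The other 2 were on 60 mg a day. The one on 60 mg once daily exceeded 8 × ULN, already a mandatory stop. The one on 30 mg twice daily had her elevation 3 weeks after the last dose. So no phase 2b case at 60 mg a day or less would have turned on the INR wording. That study also reported no clinically meaningful coagulation changes. It lasted 12 weeks and had no 45 mg arm, so it suggests rarity without giving a rate for this trial.

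**After the fix.** With INR > 1.5 everywhere, the threshold is 1.5 at every U and the lists coincide.

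**The case against.** The strongest reply is that the lists add to each other. Each requires a stop for any one of its reasons, and neither tells a site to continue a patient who falls outside it. A patient with ALT above 3 × ULN and INR 1.6 meets the Synopsis criterion and the 12.5 severe definition, so the protocol read as a whole already requires her to stop. This stands. It reduces the problem from two competing rules to the risk that a site works from 6.1 alone. That risk is real, because 6.1 is the body section on discontinuation and 5.8.2 points to it.

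The reply also relies on safeguards, and these stand too. The investigator may stop treatment at any time for safety. Under 12.5, a severe abnormality with no other cause is reported as an SAE, with immediate notice to the sponsor if the drug may be responsible, and the central laboratory issues alerts. SAP 2.2 has a liver panel monitoring liver test elevations throughout. Elevated INR is an exclusion criterion at screening. These measures limit the harm without making the stop mandatory in 6.1.

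Four stronger readings are tempting, and the documents do not support them.

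- *The bilirubin arm is weakened as well.* Without parentheses, the closing INR clause in 6.1 could be taken to apply to raised bilirubin, so that a patient with bilirubin above 2 × ULN and INR of 1.5 or less need not stop. The 12.5 table classes raised aminotransferases plus raised bilirubin as severe with no INR condition, Section 5.8.1.2 treats that combination as potential drug-induced injury, and 6.1 uses the severe label. The clause belongs to INR only.
- *Local testing makes the stop vary by site.* The protocol does allow "local lab including biochemistry, hematology, liver biochemistry and coagulation panel testing", but as a pandemic measure. Testing is central by default (Section 8.1), and the ALT, AST and bilirubin limits stay multiples of ULN under any wording.
- *A patient count can be projected from phase 2b.* A confidence limit from 12 weeks is not a maximum for 52 weeks, and it would count patients passing the aminotransferase condition rather than those in the INR gap.
- *Committee review or endpoints are affected.* Section 10.2 ties case review to the withdrawal criteria, but the SAP describes monitoring of liver test elevations without that restriction. The liver categories in SAP 6.5.2.1 contain no INR term.

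**Conclusion.** This is an internal inconsistency in a mandatory safety rule, and the INR part of the 6.1 criterion is wrong as written. It is looser than the Synopsis and the 12.5 severe definition by 0.15, 0.30 or 0.45 INR units at an assumed upper limit of 1.1, 1.2 or 1.3, and identical at 1.0 or below. The wording difference is certain. Whether it matters in practice depends on a reference range that the documents leave to the laboratory manual.

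The practical consequence is narrow: a delayed or missed stop for a patient managed from 6.1 alone, and uncertainty over whether to record deviation PD2 for her. The number of such patients is unknown and probably very small. No effect on endpoints, sample size or adverse event counts is claimed. It still merits correction, because it concerns the programme's main liver control and the remedy costs little.

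**What to change.** State the criterion once, with parentheses: ALT or AST > 3 × ULN AND (TBL > 2 × ULN OR INR > 1.5). Copy it verbatim into the Synopsis, Section 6.1, and both the severe definition and the stop list in 12.5. Section 12.5 must be included because Section 1.5 sends readers there.

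The INR limit is the sponsor's own, from the Synopsis and the severe definition. It does not move with the INR reference range and is never less protective than the 6.1 form. The parentheses also settle the reading of the bilirubin arm. It would be sensible to have the hepatic experts confirm the wording before issue.

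The cost is a clarification letter or an amendment, and possibly a few more mandatory stops. No procedures are added.
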